#### **2.4.1.2. Combination Study with Pembrolizumab**

The primary objective of Study 20150195 was to evaluate the safety, tolerability, and objective response rate (ORR) of AMB-05X administered in combination with pembrolizumab in subjects with select advanced solid tumors.

This study was conducted in 2 parts. Part 1 (phase 1b) evaluated the safety of AMB-05X in combination with pembrolizumab using a 6+3 design. The starting dose was 1400 mg AMB-05X plus 200 mg pembrolizumab every 3 weeks (Q3W). Part 2 (phase 2) further evaluated the safety and tested whether AMB-05X could enhance the antitumor activity observed historically with pembrolizumab alone and/or overcome lack of response to pembrolizumab monotherapy in subjects with select solid tumors.

A total of 15 subjects were enrolled in part 1 of the study, all of whom received  $\geq$  1 dose of AMB-05X and pembrolizumab. Subjects were treated with AMB-05X and pembrolizumab for a mean (SD) of 0.8 (0.7) months. In part 2 of the study, 101 subjects were enrolled all of whom received  $\geq$  1 dose of AMB-05X and pembrolizumab. Ninety (90) subjects received AMB-05X 1100 mg every 3 weeks plus pembrolizumab 200 mg every 3 weeks and 11 subjects received AMB-05X 1400 mg every 3 weeks plus pembrolizumab 200 mg every 3 weeks. Subjects were treated with AMB-05X and pembrolizumab for a mean (SD) of 1.6 (2.5) months.

The objective response rate was 0% in Part 1 and 3.0% in Part 2.

PK results from a total of 116 subjects were available from the study. Following administration in cycles 1 and 2, AMB-05X exposures increased in an approximately dose-proportional manner over the dose range of 1100 to 1400 mg. Mean  $C_{max}$  and mean AUC over the dosing interval  $\tau$  ( $AUC_\tau$ ) increased by 1.4- and 1.5-fold, respectively, in cycle 1 and 1.4-fold and 1.5-fold, respectively, in cycle 2, for a 1.3-fold increase in dose. Median time to reach  $C_{max}$  ( $t_{max}$ ) values ranged from 2.0 to 3.0 hours postdose in cycles 1 and 2. No significant serum accumulation of

AMB-05X was observed in subjects between cycles 1 and 2 with mean accumulation ratio for AUCτ ranging from 1.25 to 1.27.

In Part 2, 6 subjects (5.9%) who received AMB-05X 1100 mg plus pembrolizumab 200 mg had DLTs of aspartate aminotransferase increased (2 subjects) and fatigue, lipase increased, epilepsy, rash generalized, and rash maculo-papular (1 subject each). All subjects (100.0%) had  $\geq 1$  TEAA. The most common adverse events were fatigue (53.5%), periorbital edema (39.6%), anemia (37.6%), nausea (29.7%), constipation (28.7%), pyrexia (26.7%), and decreased appetite and rash (each in 25.7% of subjects). A total of 99 subjects (98.0%) had events that were  $\geq$  Grade 3, including 68 subjects (67.3%) who had Grade 4 events and 57 subjects (56.4%) who had fatal (Grade 5) adverse events. Of the fatal (Grade 5) adverse events, only tumor flare and pneumonitis (1 subject each) were considered related to study treatment. Seventy-three subjects (72.3%) had  $\geq 1$  or more SAEs. The most common SAEs were pyrexia (6.9%) and pneumonia and urinary tract infection (each in 5.0% of subjects). TEAEs considered treatment-related to AMB-05X were reported in 90 subjects (89.1%) and 86 subjects (85.1%), respectively. The most common AMB-05X-related adverse events were aspartate aminotransferase increased (53.5%), periorbital edema (38.6%), and fatigue (30.7%). Seventeen subjects (16.8%) had a treatment-emergent adverse event leading to withdrawal of investigational product. The only treatment-emergent adverse events leading to withdrawal reported in more than 1 subject were periorbital edema and pneumonitis (2 subjects each). During the study, 4 subjects (4.0%) treated with AMB-05X and pembrolizumab had liver function test results that potentially met the criteria of Hy's Law (ALT or AST  $> 3 \times$  ULN and total bilirubin  $> 2 \times$  ULN and alkaline phosphatase  $< 2 \times$  ULN). After further evaluation, none of the subjects met the definitive criteria for Hy's law. No clinically relevant trends in hematology, serum chemistry, or urinalysis laboratory values were reported.

#### **2.4.2. Intra-articular Administration of Antibodies in Clinical Studies**

There are multiple reports of the intra-articular administration of antibodies, typically into the knee for arthritic conditions, at doses ranging 10-600 mg (more commonly 100-150 mg) which

have been generally well-tolerated (Evans, 2014; Wang, 2018). Notably, there is also a case report for 100 mg bevacizumab (AvastinR, anti-VEGF) administered monthly for 1 year intra-articular to the knee of a GCT patient with no adverse local nor systemic effects (Nissen, 2014).

### **3. STUDY OBJECTIVES AND ENDPOINTS**

The objectives of this study are to evaluate the safety and efficacy of AB-05X post intra-articular injection of 150 mg biweekly for up to 12 weeks in the treatment of TGCT.

#### **3.1. Primary Endpoint**

The primary outcome measure is the frequency and severity of reported TEAEs.

#### **3.2. Secondary Endpoints**

1. The proportion of subjects who achieve an overall tumor response (objective response [OR], which includes both complete response [CR] and partial response [PR]), per the Response Evaluation Criteria in Solid Tumors Version 1.1 (RECIST v1.1) ([Eisenhauer, 2009](#)) at Week 12
2. Proportion of subjects with overall response based on TVS, a TGCT-specific method that calculates tumor volume as a percentage of the estimated maximally distended synovial activity
3. Mean change from Baseline in ROM score
4. Mean change from Baseline in the PROMIS Physical Function score
5. Mean change from Baseline in Worst Stiffness NRS score
6. Percentage of subjects who respond with a decrease of at least 30% in mean BPI score
7. Mean change from Baseline in BPI
8. Mean change from Baseline in Worst Pain NRS score
9. EQ-5D-5L Health Assessment
10. Serum and synovial CSF1 levels
11. Serum and synovial AMB-05X levels
12. Serum and synovial anti-AMB-05X antibody levels

## 4. INVESTIGATIONAL PLAN

### 4.1. Overall Study Design

This is a Phase 2, multicenter study with an adaptive design that will enroll approximately 12 subjects with TGCT of the knee for 12 weeks of multiple-dose, open-label treatment with AMB-05X.

The study schema is provided in [Section 1.2](#), and the Schedule of Events is provided in [Section 1.3](#). The subject will sign an informed consent prior to any study screening activities. There will be a screening period of up to 4 weeks, a treatment period of 12 weeks, and a post-treatment follow-up period of 12 weeks. Clinic visits will occur at Screening (Visit 1; within 4 weeks prior to Baseline); Baseline/Week 0 (Visit 2; when subjects receive their first injection of AMB-05X); Week 2 (Visit 3); Week 4 (Visit 4); Week 6 (Visit 5); Week 8 (Visit 6); Week 10 (Visit 7, when subjects receive their last injection of AMB-05X); Week 12 (Visit 8, end of treatment period and assessment of primary and secondary efficacy endpoints); Week 14 (Visit 9, for post-treatment follow-up 2 weeks after completing the treatment period); and Week 24 (Visit 10, for final post-treatment follow-up 12 weeks after completing the treatment period).

The study will begin dosing AMB-05X at 150 mg administered via intra-articular injection to the affected knee joint. Subjects will receive an injection of AMB-05X once every 2 weeks for 12 weeks (for 6 treatments total).

Tumor assessment via centrally read MRI will be performed at Screening and Weeks 6, 12, and 24. Worst pain NRS, worst stiffness NRS, PROMIS, BPI, and joint ROM will be evaluated periodically throughout the study.

Safety will be characterized, including reported AEs and SAEs and changes in physical examinations, vital signs, clinical laboratory studies (including pregnancy testing for females of childbearing potential), and ECGs.

For PK, serum AMB-05X concentrations will be measured at Week 0 (pre-dose and 2 hours after first dose), Week 2 (pre-dose [trough]), and Week 10 during steady state (including pre-dose [trough] and 2 hours after the last dose). Synovial AMB-05X concentrations will be measured at pre-dose at Weeks 0, 2, 4, 6, 8, and 10.

For PD, serum CSF1 levels will be measured at Week 0 (including pre-dose and 2 hours after first dose), Week 2 (pre-dose [trough]), and Week 10 during steady state (including pre-dose [trough] and 2 hours after the last dose). Synovial CSF1 levels will be measured at pre-dose at Weeks 0, 2, 4, 6, 8, and 10.

Serum anti-AMB-05X antibody levels will be measured pre-dose at Week 0 and Week 10. Synovial anti-AMB-05X antibody levels will be measured pre-dose at Weeks 0, 4, and 10.

Safety, PK, PD, and efficacy assessments will be reviewed by the Sponsor on a continuous, subject-by-subject basis to determine whether the assigned dose is appropriate. Depending on these results, the Sponsor may either decrease the dosage strength to 90 mg or increase the dosage strength to 210 mg in subsequent subjects who enroll. In general, subjects are expected to complete the study at the dose strength which they started the study, unless they experience a clinically significant AE that would warrant a dose reduction. As a general rule, clinically

significant AEs include, but are not limited to, any AE considered to be at least possibly related to study drug and severe in intensity or meets the criteria for a SAE. Subjects who are unable to tolerate a dosage strength of 90 mg will be withdrawn from the study

When at least 3 subjects have completed Week 6, a data monitoring committee (DMC) will review the available safety, tolerability, PK, PD, and efficacy data. Study enrollment and conduct may continue unchanged during DMC review. Based on the recommendations of the DMC, the Sponsor may then implement any one of the following adaptive changes without a protocol amendment:

- Continuation of enrollment under the existing design, without any changes to the study.
- Continuation of enrollment with a new dose or dose frequency criteria. Specifically, the DMC may recommend a dose reduction to 90 mg or a dose increase to 210 mg in subsequent subjects. Subjects may not exceed a dose of 210 mg or go below a dose of 90 mg. Subjects who are unable to tolerate a dose of 90 mg will be discontinued from the study.
- Discontinuation of further enrollment and/or suspension/termination of the study

Thereafter, the DMC should continue to review available data on a regular basis throughout the study (each time 3 subjects complete study treatment) and provide ongoing recommendations regarding appropriate next steps in study conduct (as outlined above). If a change in dose is made during the study, the DMC will again review the available data when 3 subjects have completed Week 6 at the new dose and provide further recommendations as outlined above.

[figure not shown]
Refer to [Appendix 5](#) for potential changes to study conduct in the context of COVID-19 (coronavirus disease 2019).

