#### 4.5. Subject and Study Early Termination

##### 4.5.1. End of Study Definition

A subject is considered to have completed study treatment if the subject has completed all 12 weeks of the treatment period.

A subject is considered to have completed the study if the subject has completed all study visits required for that subject, including the last follow-up visit.

The end of the study is defined as the date of the last study visit of the last subject in the study.

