### **8.3. Study Drug Administration**

After confirmation of enrollment eligibility at Visit 2 (Baseline), subjects will be enrolled into the study and receive the first dose of study drug.

The study will begin dosing AMB-05X at 150 mg administered via intra-articular injection to the affected joint. Based on ongoing review of the available safety, PK, PD, and efficacy data, the Sponsor may decrease the dose to 90 mg or increase the dose to 210 mg in subsequent subjects. A separate Study Drug Administration Instructions will be provided with detailed study drug administration procedures.

A single vial will be removed from the kit [REDACTED]

[REDACTED] prior to administration. [REDACTED] [REDACTED], diluted with [REDACTED] mL normal saline (0.9% NaCl solution), and mixed gently prior to injection. AMB-05X must be administered within [REDACTED] hours from the beginning of the warming procedure. For a dose of 150 mg, a total of [REDACTED] mL of the diluted solution will be withdrawn from the vial in a sterile syringe and administered via an intra-articular injection to the affected knee joint. For a dose of 210 mg, [REDACTED] mL of the diluted solution will be withdrawn, and for a dose of 90 mg, [REDACTED] mL of the diluted solution will be withdrawn.

Eligible subjects will receive the intra-articular injection of AMB-05X to the affected knee joint once every 2 weeks for 12 weeks (for 6 treatments total). The Sponsor may change the dose based on its own ongoing review or periodic DMC review of available data (each time 3 new subjects complete study treatment).

Study drug will be administered at the study center by qualified study staff. Subjects will remain at the study center for a minimum of 90 minutes after dosing to monitor for any adverse reactions, including any injection-site reactions.

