## 9.5. Safety Assessments

Safety and tolerability will be assessed on an ongoing basis by monitoring adverse events (AEs) (including any serious AEs [SAEs], AEs leading to withdrawal, injection-site reactions [ISRs], and any other dose-limiting toxicities [DLTs]), physical examinations/vital signs, changes in clinical laboratory values, and ECG results.

A DMC composed of qualified medical/clinical representatives will review the clinical data each time 3 new subjects complete treatment. The DMC will provide recommendations to the Sponsor regarding the acceptability of continued enrollment in the study and whether any modifications are warranted.

Safety will be assessed with the following parameters:

- Reported AEs (see [Section 9.6](#)) and concomitant medications (see [Section 7.2](#))
- Vital signs (including body weight, blood pressure, heart rate, temperature, and respiratory rate)
- Physical examination
- ECG
- Clinical laboratory tests (chemistry, hematology, and urinalysis)
- Pregnancy test

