#### **9.6.6. Serious Adverse Event Reporting and Follow-up**

Any SAE, including death, due to any cause, that occurs from the time the ICF is signed until 4 weeks after a subject's last dose of study drug must be reported to the Sponsor or its designee within 24 hours of the study center staff learning of its occurrence.

The Sponsor is required to inform worldwide regulatory authorities of SAEs that meet specific criteria and to do so in an expedited fashion. Specifically, suspected, unexpected serious adverse reactions (SUSARs) are subject to expedited safety reporting requirements. The Sponsor will report applicable SAEs to the appropriate authorities within the timelines and format required by local regulations. Therefore, the Sponsor must be notified of any SAE that occurs after informed consent is obtained within 24 hours of the study center staff learning of its occurrence.

An SAE Form must be completed and reported via email at [[contact]](mailto:[contact]). All SAEs must be recorded on the AE page of the eCRF, marking the event as serious within the form. All relevant seriousness criteria should be recorded, and relationship to study drug should be assigned at the time of initial report, as this is required to determine regulatory reporting.

SAEs must also be reported to the Institutional Review Board (IRB) / Independent Ethics Committee (IEC) according to the requirements of the IRB/IEC.

The Investigator is expected to institute appropriate diagnostic and therapeutic measures necessary to treat and promote resolution of the SAE. Any medications or procedures used to treat the SAE must be recorded on the appropriate pages of the subject's eCRF. The Investigator must determine whether the seriousness of the event warrants discontinuation of study drug.

The Investigator is expected to proactively follow up on the SAE with the subject at subsequent visits/contacts. All SAEs will be followed until no further medical intervention is warranted (e.g., the event resolves, becomes medically stable, or is assessed as chronic) or until the subject is lost to follow-up. Follow-up information on the SAE will also be reported using the AE eCRF.

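### DMC looks count only subjects who reach a visit milestone, and the dose may be raised after a related severe or serious AE before the DMC has seen it

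*Combined protocol and SAP*

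**What the plan says.** Section 4.1 and the synopsis set three kinds of DMC look.

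- First look: "When at least 3 subjects have completed Week 6, a data monitoring committee (DMC) will review the available safety" data. The same review also takes in efficacy, PK and PD.
- Recurring looks: Section 9.5 says that the DMC "will review the clinical data each time 3 new subjects complete treatment". Section 4.5.1 defines this: "A subject is considered to have completed study treatment if the subject has completed all 12 weeks of the treatment period".
- After a dose change: a further look is due "when 3 subjects have completed Week 6 at the new dose".

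No section provides for an unscheduled look after an adverse event.

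Section 4.1 also names an open-ended class of clinically significant AE. The part that it spells out is "any AE considered to be at least possibly related to study drug and severe in intensity or meets the criteria for a SAE". The only stated use of this class is as a general rule for reducing the dose of the affected subject.

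Dose changes for later subjects have two routes. One follows a DMC recommendation (Section 4.1). The other does not need one. Sections 4.1 and 4.4 allow a move to 90 mg or 210 mg on the Sponsor's continuing review, and Section 8.3 states: "The Sponsor may change the dose based on its own ongoing review or periodic DMC review of available data".

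**The concern.** Two rules work against early independent review when there is early toxicity. A subject who leaves treatment because of a drug-related event in the first weeks never becomes one of the three whose progress triggers the look, so the look comes later in the situation where it is most wanted. And the class of event that the protocol itself treats as clinically significant places no condition on a dose increase for the next subjects.

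The stakes are moderate but real. TEAEs are the primary endpoint (Section 3.1). AMB-05X has not been given into the joints of TGCT patients (Section 4.2). The intra-articular data for this drug are one injection per knee in 4 monkeys, at human-equivalent doses of about 100 mg and about 160 mg (Section 2.3.4). On that scale, 210 mg lies above the highest intra-articular dose of AMB-05X that the protocol reports.

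**Working it through.** **Step 1. Who counts, from Sections 4.1, 4.5.1 and 9.5.**

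| Subject | Counts toward a Week 6 look | Counts toward a recurring look | Data seen at the next look |
|---|---|---|---|
| Stops before Week 6 | No | No | Yes |
| Stops after Week 6, before the end of the 12 weeks | Yes | No | Yes |
| Reduced from a new dose before Week 6, stays on treatment | Not for the look at that dose, on a plain reading | Yes, if all 12 weeks are completed | Yes |

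The last column follows because each look covers the data available at that time. Section 4.5.2 also asks early stoppers to complete Visit 8/ET and Visit 9.

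**Step 2. Effect on the first look.** The protocol gives no accrual rate. Assume even accrual at r starts per month of 30.4 days, first start on day 0, all other subjects reaching Week 6 on day 42 of treatment, and a look on the day its condition is met. The accrual interval is i = 30.4 / r. With s of the first three subjects stopping before Week 6:

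- day of first look = (2 + s) × i + 42
- subjects started by then = floor(day / i) + 1

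| Starts per month | i (days) | s = 0: day (started) | s = 1: day (started) | s = 2: day (started) |
|---|---|---|---|---|
| 1 | 30.4 | 102.8 (4) | 133.2 (5) | 163.6 (6) |
| 2 | 15.2 | 72.4 (5) | 87.6 (6) | 102.8 (7) |
| 3 | 10.1 | 62.3 (7) | 72.4 (8) | 82.5 (9) |
| 4 | 7.6 | 57.2 (8) | 64.8 (9) | 72.4 (10) |

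Example at 2 per month: 2 × 15.2 + 42 = 72.4 days with no stop, and 3 × 15.2 + 42 = 87.6 days with one. Each stop adds one interval, 7.6 to 30.4 days, and one more start. If stops counted, the first look would fall no later than the s = 0 column.

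**Step 3. Effect on the recurring looks.** Among 12 subjects with k stopping early and none replaced, the number of looks is floor((12 − k) / 3): 4 for k = 0, 3 for k = 1 to 3, and 2 for k = 4 to 6.

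**Step 4. How likely a delay is.** If each subject independently has chance q of stopping before Week 6, the chance that at least one of the first three does so is 1 − (1 − q)³. This is 0.14, 0.27 and 0.49 at assumed q of 5%, 10% and 20%. The nearest figure in the protocol is 1 of 25 subjects (4%) who discontinued for a treatment-related AE in the IV monotherapy study (Section 2.4.1.1). That gives 1 − 0.96³ = 0.12, but by another route, in advanced cancer and without the Week 6 limit.

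**Step 5. Dose increase.** No arithmetic applies. Under Sections 4.1, 4.4 and 8.3, a related severe AE in an early subject may be followed by 210 mg in the next, with no DMC contact in between. The documents give no basis for estimating how likely that is.

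**The case against.** The strongest reply is that oversight does not rest on the DMC alone. The Sponsor reviews each subject continuously and dose changes depend on those results. There is one step up, capped at 210 mg, and a new dose triggers its own look. SAEs reach the Sponsor within 24 hours and go to the IRB/IEC (Section 9.6.6). The Investigator can act too: "The Investigator must determine whether the seriousness of the event warrants discontinuation of study drug". The Sponsor or a regulator can stop the study (Sections 4.5.3 and 12.7), and nothing forbids an unscheduled DMC meeting. Other antibodies have been given into joints at 10 to 600 mg and were generally well tolerated (Section 2.4.2), and the IV monotherapy study had no treatment-related serious AE. The separate SAP (Section 10.1) or a DMC charter was not available and could hold a rule.

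All of this stands, and it rules out three stronger readings.

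- A reader might infer that toxicity stops escape DMC review. They do not: the data are in the next look, and a stop after Week 6 still counts toward a Week 6 look.
- A reader might take the subjects started before the first look as unreviewed exposure. They are only starts before a DMC look, because the Sponsor reviews throughout.
- A reader might infer that dose increases are uncontrolled. They follow a Sponsor review of safety, PK, PD and efficacy; what is missing is a required DMC step.

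None of the safeguards requires the DMC to be told of a related severe or serious AE, or to reply before an increase. A limit on an authority that the protocol grants belongs in the protocol.

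**Conclusion.** The point holds on the text. The counting rule can delay independent review after early toxicity, and the Sponsor may raise the dose without DMC advice after a related severe or serious AE. The measurable part is modest: about 8 to 30 days and one more start for each stop before Week 6 among the first three subjects. It rests on assumed even accrual of 1 to 4 starts per month, with all other subjects reaching Week 6. The dose-increase gap is the more serious part and has no figure. Neither part shows that subjects would go unmonitored. This is a cheap improvement.

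**What to change.** Add to Section 4.1 and the synopsis:

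> A subject who discontinues study drug, or whose dose is reduced, because of an AE at least possibly related to study drug counts toward the 3 subjects for the next DMC review.

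> Any AE at least possibly related to study drug that is severe or meets SAE criteria will be sent to the DMC within [7] calendar days, and the dose will not be increased for subsequent subjects until the DMC has replied.

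Repeat the limit on dose increases in Sections 4.4 and 8.3. The bracketed time is for the Sponsor and DMC to set.

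State openly that this trigger requires relatedness for both branches. The wording in Section 4.1 is ambiguous on whether an unrelated SAE belongs to the class, and the new sentence settles that for the trigger only. The broader, open-ended class should stay in place for dose reduction in the individual subject.

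Cost: two sentences and two cross-references. The DMC exists, and severity, seriousness and relatedness are already recorded for each AE (Section 9.6.5). Expected affected subjects among 12 are 12 × p, or 0.6, 1.2, 2.4 and 4.0 at assumed rates of 5%, 10%, 20% and 33%, so a few extra DMC communications. The severe category includes events that interrupt daily activities (Section 9.6.3.1), so a knee flare after injection could qualify. A dose increase may be briefly delayed, and some looks will rest on fewer than 3 Week 6 MRIs. Enrolment at the current dose, ongoing treatment and dose reductions are unaffected.
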